9.2 Recording Adverse Events

The Imperial Clinical Trials Unit (ICTU) has been delegated by the Sponsor to undertake all sponsor duties relating to pharmacovigilance.

All non-serious AR/AEs, whether expected or not, should be recorded in the adverse event section of the relevant Case Report Form. All new SAEs regardless of causality, occurring after the patient has signed informed consent and until the last patient visit must be reported to ICTU within 24 hours of learning of its occurrence and must also be recorded on Adverse Event Case Report Form (AE CRF) within the InForm database

Recurrent episodes, complications, or progression of the initial SAE must be reported as follow-up to the original episode, regardless of when the event occurs. This report must be submitted according to the study specific reporting procedures.

An SAE that is considered completely unrelated to a previously reported one should be reported separately as a new event.

At each contact with the subject during the treatment period, the Investigator must seek information on adverse events by specific questioning and, as appropriate, by examination. Information elicited should be recorded immediately in the source document, and the AE CRF. All clearly related signs, symptoms, and abnormal diagnostic procedures results should be recorded in the source document using the event terms and grading given in the relevant eCRF pages.

The clinical course of each event should be followed until resolution or stabilisation.

9.2.1 Exclusions to Adverse Event Recording Requirements

Many clinical events are likely to occur which would ordinarily need recording as adverse events. However, events that are recognised and expected complications of the condition (listed in Appendix 1) are exempt from the normal recording procedures, unless they become 'serious' by definition (section 9.1).

9.3 Pre-existing Conditions

A pre-existing condition should not be reported as an AE unless the condition worsens during the trial. The condition, however, must be reported in the Medical History Form.

9.4 Reporting of Serious Adverse Events (SAEs, SARs and SUSARs)

All serious adverse events and reactions must be reported immediately by the Principal Investigator or delegate to the ICTU. In turn, ICTU will inform the Sponsor (within 24hrs of becoming aware of the event) and the Funder (as soon as becoming aware and not more than 15 calendar days).

[figure not shown]
Summary of product characteristics (SmPC) should be used as the Reference Safety Information. Serious adverse events expected to occur with Canakinumab should be recorded on an SAE/SUSAR Report Form on InForm and the ICTU/Sponsor informed within 24 hours. A submitted SAE form on InForm will automatically send alert emails to the Chief Investigator, the Project Manager and the Sponsor. Adverse Events considered to be expected for Reporting purposes are detailed in Appendix

2. These reports should be followed by further detailed SAE/SUSAR Report Forms until resolution of the event.

N.B. The SAE/SUSAR Report Form should be completed as though the patients were taking active form of IMP, even though all parties are blinded.

Study specific SAE reporting instructions will be available and provide full detail on reporting requirements. An overview of the Safety Reporting Process is detailed in the diagram below.

Safety Reporting Overview

Contact details for reporting SAEs and SUSARs

Follow the study specific procedure for reporting SAEs and SUSARs and complete an SAE form & submit to the Study Coordination Centre (ICTU) as soon as possible (within 24 hrs). SAE forms are available on the InForm eCRF system.

ICTU Trial Manager: [contact]

Sponsor's contact: [contact] (contact only by ICTU)
Funder's contact: [contact] (contact only by ICTU)

9.5 Post-treatment SAEs & Follow-Up

The reporting requirement for SAEs affecting subjects applies for all events occurring up to the patients last study visit.

All unresolved adverse events (serious and non-serious) should be followed up by the Investigator until the events are resolved, the subject is lost to follow-up, or the adverse event is otherwise explained. At the last scheduled visit, the Investigator should document any ongoing AEs/SAEs, and these should be managed as per local practice.

The Investigator should notify the ICTU of any death or adverse event occurring at any time after a subject has discontinued or terminated study participation that may reasonably be related to this study.

9.6 Pregnancy

If a subject or his partner becomes pregnant whilst taking part in the trial or during a stage where the foetus could have been exposed to an IMP, the Investigator must ensure that the subject and the subject's healthcare professional are aware that follow-up information is required on the outcome of the pregnancy. If the subject leaves the area, their new healthcare professional should also be informed. Each pregnancy occurring while the patient is on study treatment must be reported to ICTU within 24 hours of learning of its occurrence. Any SAE experienced during the pregnancy and unrelated to the pregnancy must be reported on a SAE form. The pregnancy should be followed up to determine outcome, including spontaneous or voluntary termination, details of the birth, and the presence or absence of any birth defects, congenital abnormalities, or maternal and/or newborn complications. Pregnancy follow-up should be recorded on the same form and should include an assessment of the possible relationship to the investigational treatment.

Study treatment for pregnant participants must be discontinued immediately.

Contraception

The following methods of contraception are accepted:

- (i) Total abstinence (when this is in line with the preferred and usual lifestyle of the subject). Periodic abstinence (e.g., calendar, ovulation, symptothermal, post-ovulation methods) and withdrawal are not acceptable methods of contraception.
- (ii) Female sterilization (have had surgical bilateral oophorectomy with or without hysterectomy) or tubal ligation at least six weeks before taking study treatment. In case of oophorectomy alone, only when the reproductive status of the woman has been confirmed by follow up hormone level assessment.
- (iii) Male sterilization (at least 6 months prior to screening). For female subjects on the study, the vasectomized male partner should be the sole partner for that subject.
- (iv) Barrier methods of contraception: Condom or Occlusive cap (diaphragm or cervical/vault caps) with spermicidal foam/gel/film/cream/ vaginal suppository.
- (v) Use of oral, injected or implanted hormonal methods of contraception or placement of an intrauterine device (IUD) or intrauterine system (IUS) or other forms of hormonal contraception that have comparable efficacy (failure rate <1%), for example hormone vaginal ring or transdermal hormone contraception. In case of use of oral contraception women should have been stable on the same pill for a minimum of 3 months before taking study treatment.

Reliable contraception should be maintained throughout the study.

9.7 Evaluation of SAEs

The Principal Investigator should ensure that each SAE is identified and assessed for the likelihood of the event being a response to an IMP. Once reported to the ICTU, the event will also undergo a review of the evaluation of seriousness, expectedness and causality. Investigator reports of suspected SARs will be reviewed and those that are SUSARs, identified and reported to the UK regulatory authority (MHRA).

In the event of a possible SUSAR, the Clinical Reviewer may contact the local PI to discuss the causality assessment.

9.7.1 Causality of AEs

The relationship of an AE to the IMP should be graded by the investigator responsible for the care of the participant as follows:

Definitely related:

- Starts a reasonable time after the study drug administration;
- Stops/improves when the study drug has been stopped;
- Can reasonably be explained by known characteristics of the study drug.

Probably related:

- Starts a reasonable time after the study drug administration;
- Stops/improves when the study drug has been stopped;
- Cannot be reasonably explained by known characteristics of the patient's clinical state.

Possibly related:

- Starts a reasonable time after the study drug administration but could have been produced by the subject's clinical state or other modes of therapy administered to the patient.

Unlikely to be related:

- The time association or the patient's clinical state is such that the study drug is not likely to have had an association with the observed effect.

Unrelated:

- The AE is definitely not associated with the study drug administered.

If any doubt about the causality exists the local investigator should inform the study coordination centre who will notify the Chief Investigator. The pharmaceutical companies and/or other clinicians may be asked to advise in some cases.

In the case of discrepant views on causality between the investigator and others, all parties will discuss the case. In the event that no agreement is made, the MHRA will be informed of both points of view.

9.8 Expedited Reporting

The ICTU will report SUSARs to the regulatory authorities (MHRA and the relevant ethics committees) as follows:

- SUSARs which are fatal or life-threatening will be reported within 7 calendar days of the CTU first becoming aware of the reaction. Any additional relevant information must be reported within a further 8 days (i.e. by day 15).
- SUSARs that are not fatal or life-threatening will be reported within 15 days of the CTU first becoming aware of the reaction.

9.9 Annual reporting of Serious Adverse Events

Annual Safety reports will be submitted to the Sponsor, the Ethics Committee and Regulatory Authority in accordance with regulatory requirements.

Novartis Pharmaceuticals UK Limited will be responsible for submission of the Development Safety Update Report (DSUR). The Sponsor (via ICTU) will provide information required by Novartis to include the study in the Novartis DSUR in an integrated manner. Novartis will provide a copy of the submitted DSUR to ICTU for filing in the study TMF.

9.10 Reporting urgent safety measures

If any urgent safety measures are taken the CI/Sponsor shall immediately and in any event no later than 3 days from the date the measures are taken, give written notice to the relevant REC of the measures taken and the circumstances giving rise to those measures.

10. Patient Loss from Study Post-Randomisation

The PI will make every reasonable effort to keep each patient on study.

10.1 Patients lost

The following 3 sub-sections describe patients that will be regarded as having been lost from the study, i.e. no further follow-up visits will take place and no further data will be collected;

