7.5 Schedule of Assessments

Table 1 lists all of the assessments and indicates with an ‘x’ at which visits the assessments are performed. Patients should be seen for all visits on the designated day, or as close to it as possible – the visit window/tolerance for each visit is given below the table. At a minimum, patients will be contacted for safety evaluations during the 90 days following randomisation to the study. At this final visit the adverse event and concomitant medications should be reconciled on the CRF. Documentation of attempts to contact the patient should be recorded in the source documentation.

Table 1: Assessment schedule

| | Screening | Baseline 6, 9, 11 | Day 7 ⁴ | Day 14 ⁴ | Day 21 ⁴ | Day 28 ^{2, 11} | Day 42 ^{1, 4} | On Discharge ¹⁰ | Day 90 ³ | Unscheduled |
|--|----------------|----------------------|--------------------|---------------------|---------------------|-------------------------|------------------------|----------------------------|---------------------|-------------|
| Informed Consent | X | | | | | | | | | |
| Demographic data | X | | | | | | | | | |
| Inclusion/Exclusion criteria | X | X | | | | | | | | |
| HIV test [^] | X | | | | | | | | | |
| Pregnancy test ⁺ | X ⁵ | | | | | | | | X | |
| Hepatitis B & C serology[^] | X | | | | | | | | | |
| Genetic sequencing (PNPLA3) | X | | | | | | | | | |
| Urinary ethyl glucuronide | X | X | | | | X | X | | X | |
| Alcohol consumption | X | | | | | X | X | | X | |
| Duration since admission to hospital | | | X | | | | | | X | |
| Medical history | X | | | | | | | | | |
| Prior/Concomitant medications | X | X | X | X | X | X | X | X | X | |
| Vital signs | X | X | X | X | X | X | X | X | X | X |
| Physical exam | X | X | X | X | X | X | X | X | X | |
| Weight | X | | | | | X ¹ | | X | X | |
| Height | X | | | | | | | | | |
| Calorie and protein intake | | X | X | X | X | X | X | X | X | |
| Randomisation | | X | | | | | | | | |
| IMP / placebo administration | | X | | | | X | | | | |
| Prothrombin time | X | X | X | X | X | X | X | X | X | |
| Haematology [%] | X | X | X | X | X | X | X | X | X | X |
| Clinical chemistry [%] | X | X | X | X | X | X | X | X | X | X |
| Serum CK18-M30/M65 sample | | X | X | X | X | X | X | X | X | |
| DF, MELD, GAHS scores | X | X | X | X | X | X | X | X | X | |
| Lille score | | | X | | | | | | | |
| Overt GI Haemorrhage assessment [§] | X | X | X | X | X | X | X | X | X | |

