| Acute kidney injury assessment [§] | X | X | X | X | X | X | X | X | X | |
| EDTA sample for DNA (16S) | X | X | X | X | X | X | | | X | |
| PBMC sample [~] | | X | X | X | | X | | | X | |
| Infection/ Sepsis/ SIRS screen | X | X | X | X | X | X | X | X | X | X |
| USS Liver assessment [§] | X | | | | | | | | | |
| Fibroscan measurement [§] | | X | | | | X | | | X | |
| Gene expression sample | | X | | | | X | | | | |
| Liver biopsy (incl. HVPG measurement [*]) [§] | | | X | | | X | | | | |
| Adverse events | | X | X | X | X | X | X | X | X | |
| PK/PD samples in blood and ascites fluid # | | X | X | X | X | X | X | | X | X |
| Biomarker serum | | X | X | X | X | X | X | X | X | |
| Stool & saliva sample | | X | | X | | X | | | X | |

Footnotes to Schedule of Assessments

| | | |
|---------------|--|---|
| ¹ | Day 42 visit | Required for patients who received second dose study drug at Day 28 |
| ² | Day 28 visit | A Day 28 assessment/follow up treatment/biopsy can be performed between Day 25 and Day 35 |
| ³ | Day 90 visit | A Day 90 assessment can be performed 14 days either side of the target date |
| ⁴ | Day 7, 14, 21, 42 visits | For Day 7, 14, 21 and 42 assessments a tolerance of 48 hrs in time window either way is accepted |
| ⁵ | Screening pregnancy test | Needs to be performed as serum test |
| ⁶ | Screening and baseline samples | If baseline visit is performed within 72 hours since screening, then screening samples which repeat at baseline may be accepted on baseline date. |
| ⁷ | Screening and Baseline visit | The maximum time between screening and date baseline is 7 days |
| ⁸ | Baseline liver biopsy acceptance window | The maximum timeframe for a baseline biopsy to be accepted into the trial is 7 days before baseline visit (day of Randomisation and study drug administration). |
| ⁹ | Baseline visit | Allowance of -1 day is accepted to allow for blood results to come through for re-confirmation of eligibility before randomisation and IMP/Placebo administration. Baseline date of visit should always be the date of randomisation and IMP administration. |

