| ¹⁰ | Discharge | Patients who are discharged during the follow-up period are not required to attend further weekly visits other than on Day 28 (when the potential second IMP dose and second biopsy is taking place), Day 42 (if second Imp dose was administered) and Day 90, which is the end of study visit. Patients due to be discharged will have the samples collected on discharge, as specified in the schedule of assessments below |
| ¹¹ | Baseline; Day 28 | Sample collection is pre-IMP administration. |
| # | Pharmacokinetic and pharmacodynamics samples - blood and ascitic fluid | In case of ascites, ascites fluid sample needs to be collected only once, at the time when patient is having ascites tapped for clinical purposes. |
| * | TJ liver biopsy | HVPG measurement should be collected in all TJ liver biopsies. |
| ^ | Virology screening | Results within 6 months of screening may be accepted without the need to repeat |
| + | Screening and Day 90 pregnancy tests | Pregnancy test required only for females of reproductive age only |
| ~ | PMBC | PBMC, which are to be sent to a central lab immediately after collection, should not be collected on Friday or Saturday in order to avoid loss of sample due to a weekend staff cover at the central laboratory. When PMBCs are posted out, an email notification must be sent, as per study Lab Manual. |
| % | Haematology & Biochemistry | ± 1 day of screening date |
| \$ | Overt GI haemorrhage assessment, AKI assessment; Fibroscan, USS | From day of admission onwards |

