10.1.2 Lost to follow-up

These are patients who do not attend a follow-up assessment after site staff have attempted to contact the patient at least twice, e.g. by telephone.

As these patients have not withdrawn their consent, the data already collected for them may be used and therefore needs returning in the usual manner.

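### Day 90 mortality and, to a lesser degree, the 90-day event endpoints can be incompletely ascertained: unreachable patients get no vital-status check, and a final visit from Day 76 ends routine SAE reporting

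*Combined protocol and SAP*

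**What the plan says.** Section 3.3 lists mortality at Day 90 as a secondary endpoint. It also lists infection and sepsis, acute kidney injury, and variceal haemorrhage, ascites or encephalopathy, each over 90 days.

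**Lost patients.** Section 10.1 says that for patients regarded as lost, "no further follow-up visits will take place and no further data will be collected". Section 10.1.2 defines one such group: "These are patients who do not attend a follow-up assessment after site staff have attempted to contact the patient at least twice". It adds: "As these patients have not withdrawn their consent, the data already collected for them may be used". Section 12.11 provides for a letter telling the GP about participation. It does not provide for collecting outcomes from the GP.

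**Visits after discharge.** Footnote 10 of the schedule in Section 7.5 says: "Patients who are discharged during the follow-up period are not required to attend further weekly visits other than on Day 28", with Day 42 (if re-dosed) and Day 90 as the other exceptions. Footnote 1 describes the Day 42 visit as "Required for patients who received second dose study drug at Day 28".

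**The final visit.** Footnote 3 says: "A Day 90 assessment can be performed 14 days either side of the target date". Section 7.5 says: "At this final visit the adverse event and concomitant medications should be reconciled on the CRF". Section 9.5 says that the SAE reporting duty "applies for all events occurring up to the patients last study visit", and Section 9.2 sets the same end point. After participation ends, Section 9.5 asks for notification only of deaths or events that may be related to the study.

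**Mitigating text.**
- Section 7.5 asks for visits as close as possible to the target day, and for safety contact during the 90 days, without giving times.
- Section 9.2 keeps complications or progression of an earlier SAE reportable whenever they occur.
- Section 9.5 asks for unresolved adverse events to be followed.
- Section 10 asks for every reasonable effort to keep patients on study.

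**The concern.** A site that follows these rules exactly can finish with patients whose status at Day 90 is unknown, in two ways.

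First, a discharged patient who is not re-dosed has no scheduled visit between Day 28 and Day 90. If that patient misses Day 90 and cannot be reached, collection stops and the last scheduled observation was at Day 28. A patient who has died at home also fails to attend, so this kind of loss may be related to the outcome.

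Second, all-cause mortality at Day 90 should not depend on a judgement about relatedness. For a patient whose final visit is on Day 76, however, reporting of a new death on Day 85 does depend on one, unless the death continues an earlier SAE.

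The Day 28 to Day 90 period matters in this trial. The background in Section 2 says that the early survival benefit of prednisolone is gone by 90 days because of infection, and Section 2.5 accepts that canakinumab may raise infection risk. Section 8.2 leaves missing-data methods to a separate analysis plan, but no analysis can recover a status that was never collected.

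**Working it through.** **Inputs from the protocol.** 52 patients, 26 per arm, and a 10% drop-out allowance (Section 8.1); 22% mortality at 90 days for mDF ≥ 32 and MELD ≤ 27 (Section 2); visit windows (Section 7.5). The documents give no loss rate between Day 28 and Day 90, so 5%, 10% and 20% are assumptions. The timing of deaths is also assumed: a constant hazard, with front-loaded alternatives.

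**Plan's own figure.** The protocol gives no figure for completeness of follow-up. Its sample size reproduces: 40% versus 80%, two-sided 5%, 80% power, no continuity correction gives 23 per arm, 46 in total. 46/0.9 = 51.1, hence 52 in two equal arms. Nothing below changes it.

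**Gap between scheduled visits** (discharged, not re-dosed). Nominal: 90 − 28 = 62 days. With the windows: 76 − 35 = 41 days to 104 − 25 = 79 days.

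**Hazard.** h = −ln(0.78)/90 = 0.002761 per day. Expected deaths: 0.22 × 52 = 11.4.

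**Route 1, lost and unreachable.**
- P(death by Day 90 | alive at Day 28) = 1 − exp(−62h) = 0.157.
- Lost at 5%, 10%, 20% of 52: 2.6, 5.2, 10.4 patients. Deaths of unknown status: 0.41, 0.82, 1.64.
- Last seen at Day 42 instead, 10% lost: (1 − exp(−48h)) × 5.2 = 0.124 × 5.2 = 0.65.
- Front-loaded, with a fraction f of the 90-day deaths before Day 28, the risk is 0.22(1 − f)/(1 − 0.22f). This is 0.124 for f = 0.5 and 0.078 for f = 0.7. Times 5.2: 0.64 and 0.41.
- Extreme bounds: 5 of 52 unknown and 10 deaths among the 47 known give overall mortality between 10/52 = 19.2% and 15/52 = 28.8%.
- For scale, the 95% half-width for the difference between arms, with 22% in both, is 1.96 × √(2 × 0.22 × 0.78/26) = 0.225, or 22.5 points.

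**Route 2, early final visit.** The window runs from 90 − 14 = Day 76 to 90 + 14 = Day 104.
- Visits spread evenly over the 28 days: (1/28) × ∫ from 76 to 90 of (exp(−ht) − 0.78) dt = 0.00763. Times 52: 0.40 deaths.
- Front-loaded, constant hazard after Day 28: 0.31 (f = 0.5) and 0.19 (f = 0.7).
- Every visit on Day 76: (exp(−76h) − 0.78) × 52 = 0.0307 × 52 = 1.6. Section 7.5 asks for the opposite.

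The Route 2 figures are upper limits for the visit pattern assumed, because deaths that may be related to the study, or that are progressions of an earlier SAE, stay reportable.

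**The case against.** The strongest reply is that the protocol closes most of this gap itself. A patient becomes lost only after at least two contact attempts. For a missed Day 90 visit, those attempts fall near Day 90, and if a call reveals a death the patient belongs under Section 10.1.3. For patients who attend, nothing between Day 28 and Day 90 is lost for lack of a visit, because events are reconciled at the final visit. Progression of an earlier SAE and possibly related deaths stay reportable after it. This stands, and it confines the problem to patients who cannot be reached or were lost earlier, and to new, unrelated events after an early final visit. The promised safety contact does not close what remains: it has no stated timing and conflicts with the stop on data collection in Section 10.1.

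A second reply is that the numbers are small and partly borrowed. This also stands. The 10% comes from the allowance for the biopsy endpoint and may include deaths: at the assumed hazard, 1 − 0.78^(28/90) = 7.4%, or about 3.9 of 52, would die by Day 28. The 19.2% to 28.8% range treats all five unknown patients as dead at one end, whereas about 0.8 deaths would be expected among 5.2.

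A third reply is that a telephone call cannot establish acute kidney injury (Section 7.6.6) or the culture-, assay- or imaging-based infections in Section 7.6.7. This is correct, and the fix is limited accordingly.

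A reader might go further and infer that vital status is never sought, that every event after the final visit goes unreported, or that the mortality comparison is biased towards one arm. The documents support none of these. Contact attempts and two continuing reporting duties are written in, and nothing indicates that losses or early visits would differ between arms in this double-blind trial.

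**Conclusion.** The point holds in limited form. Followed as written, the plan can leave Day 90 mortality incomplete, and the 90-day event endpoints to a lesser degree.

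The likely size is about 0.4 to 1.6 deaths of unknown status for assumed losses of 5% to 20% at Day 28, and at most about 0.4 of 11.4 expected deaths missed through an evenly used visit window. The second figure falls if visits cluster near Day 90 as Section 7.5 asks. Both rest on 22% mortality and a constant hazard; front-loaded deaths make them smaller. The loss rates are assumptions.

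These amounts are small beside the sampling uncertainty of a trial with 26 patients per arm, and the direction of any bias is unknown. The primary histology endpoint and the sample size are not affected. This is a worthwhile, inexpensive improvement to secondary endpoints and not a threat to the trial's main conclusion.

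**What to change.** Amend Sections 10.1 and 10.1.2, footnote 3 of Section 7.5, and Section 9.5 as follows:

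1. For every randomised patient who has not withdrawn consent and is due Day 90 follow-up, ascertain vital status on or after Day 90. Include patients lost to follow-up and those whose final visit came before Day 90. Use the telephone or, where consent allows, GP or hospital records.
2. Take the 90-day clinical events from hospital records where available, since a call alone is not enough for acute kidney injury or for infections defined by culture, assay or imaging.
3. State that all 90-day endpoints are cut at Day 90 for patients seen later, so that events on Days 91 to 104 are not counted.

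The cost is a few calls or record checks and a protocol amendment with its approvals across sites. There are no extra visits or biopsies. The consent text is not available for this review, so whether it already covers outcome collection from records must be checked; wording is added only if it does not.

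A separate point for reconciliation is the follow-up of histology-negative patients. Section 10.2 gives 28 days of safety follow-up, Section 7.5 sets safety contact over 90 days as a minimum without exception, Section 1.7 gives no duration, and Sections 3.6 and 8.1 describe these patients as withdrawn. Section 10.2 may be a deliberate exception, but Section 7.5 does not say so. The amended text should also state whether this group enters the analysis of the 90-day safety outcomes.
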